* Subjects should have been using at least 100mg of methamphetamine (not prescribed), 5 days per week for at least one year

* Abstinent from methamphetamine for 48 hours on days of scans

CS groups:

• At least one exposure to a stimulant, either recreational or prescribed

Criteria for Exclusion:

All groups:

- * Allergies to stimulants or hypersensitivity to taking a stimulant in the past
- * Diagnosis of a psychotic or mood disorders (past diagnoses of depression allowed) (DSM-V)
- * Self-reported claustrophobia
- * Women who are pregnant or breast-feeding

* Positive urine drug screen result at any point during the study (except for amphetamines except for verified medical reason)

* Intoxicated on study days (see Abstention from Methamphetamine below)

* Clinically significant neurological, cardiovascular, endocrine, renal, hepatic or systemic disease that could compromise safe participation or confound outcomes (including hepatitis C, HIV, severe anemia, or liver disease)

* History of glaucoma

- * Metal in the body which is contraindicated for MRI or would compromise image quality
- * Current prescription use of stimulants, anti-psychotic drugs or anti-Parkinson's drugs
- * Use of monoamine oxidase inhibitors within 14 days
- * Use of serotonin reuptake inhibiters, serotonin norepinephrine reuptake inhibiters, triptans, tricyclic

antidepressants, Fentanyl, lithium, tramadol, tryptophan, bispurone, St. John's Wort, insulin, phenothiazines, guanethidine, acidifying/alkalinizing agents, CYP2D6 inhibitors, proton pump inhibitors

MUD Groups:

- Positive urine drug screen at any point during the study (except for meth or marijuana)
- History of any severe substance use disorders within the last 5 years, except for methamphetamine use disorder or tobacco use disorder

CS Groups:

- History of any severe substance use disorders within the last 5 years except tobacco use disorder
- Positive urine drug screen at any point in the study (except for marijuana or verified medical reason)

Enrollment: We will enroll up to 200 individuals into Part 1. Individuals will then be screened into Part 2 based on their genotype and if they have no contraindications for methamphetamine administration or MRI. Subjects must have the WT Group or CV Group to screen into Part 2 and we will continue to enroll subjects into Part 2 until we have 18 completers in each of the 4 WT and CV groups.

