Abstention from Methamphetamine: MUD subjects will be asked to abstain from using methamphetamine on the day of Visit 1 and 2 will be asked to abstain from using methamphetamine for 24 hours prior to Visits 3 and 4. If subjects come to their appointments intoxicated, they may be dropped from the study or rescheduled. **Subject selection and randomization:** [name] laboratory at the Portland VA will genotype the *htaar1* in Part 1 participants to identify all V288V variants (members of the [name] lab may also prep samples but will not read results). The CV Groups will be composed of subjects who are heterozygous or homozygous for the CV SNP without any other variant, while the WT Groups will include those who have the wild type genotype. The *htaar1* gene will also be sequenced in its entirety (the [name] lab will purify the DNA and then send it to the OHSU Core lab) so that individuals with rare non-synonymous *taar1* can be identified *post hoc* and analyzed separately. We will screen subjects until we have 18 subjects in each of the four CV Groups and the WT Groups balanced by age and sex (a research assistant not involved in the subject evaluations will check the balance and will adjust accordingly). As the population gene frequency is 23%, we expect to

Visit Number	1	2	3	4
	Part 1		Part 2	
Informed Consent	\checkmark			
Review Study Eligibility	✓			
Medical History	✓			
Family History	✓			
Neuropsych Assessment		✓		
Computer Tasks		✓		
Vital Signs	✓		✓	✓
Urine Drug Screen/Pregnancy		1		
Test	v	•	v	v
Cheek Swabs	✓			
EKG	✓			
Study Drug or Placebo				
Administered			v	v
MRI Scans			✓	✓
Blood Draw	✓		✓	✓
Saliva Collection	✓		✓	✓
Questionnaires		✓	✓	✓
Total Time (hours)	3	3	8	8

genotype up to 200 individuals to ensure two groups of age and gender matched subjects. We will replace dropouts until we have 18 completers in each group (for a total of 72 completers). The study team will be blind to genotype. The [name] lab will determine genotype and refer subjects back to the study team for inclusion in blocks of six subjects (three CV and three WT). If more than three CV or WT subjects are genotyped before three of the other group, then participants will wait for enrollment into Part 2 until the current block of six subjects is complete. Genotype data will be provided to the pharmacy to allow stratification by genotype during randomization.

Visit Schedule

Part 1: Visits 1 and 2: Consent/Screening: Subjects will be consented and then screened for

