Part 2: Visits 3 and 4: Scan Days: All study procedures will happen at the Portland VA except for the MRI scans which will take place at the OHSU AIRC. MA administration and questionnaires may take place at either the VA or OHSU. Subjects are asked to abstain from MA for 72 h before the scan. A urinalysis will be performed to ensure that women are not pregnant and that no other drugs are present. Subjects will undergo a baseline MRI scan approximately 1 hour after the start of each visit followed by drug administration (placebo or MA) and a second scan 1.5 hours after that. Blood samples (3 mL) and/or oral fluid samples will be drawn before drug administration and after the second scan to quantify MA levels. At the Portland VA, during visit 2, up to 15 mL blood will be drawn and a cheek swab will be taken and both will be stored in the MARC biorepository located at the Portland VA. Blood may be stored as plasma or whole blood. Surveys and neurocognitive assessments will be performed before and after each scan at the Portland VA. Pulse, respiration, and pulse oximetry will be monitored throughout each scan. Each visit will last approximately 8 hours, and the subjects will be monitored (blood pressure, heart rate) closely throughout. The Systematic Assessment for Treatment Emergent Effects (SAFTEE) will be used to screen for adverse effects at the end of the day and the individual will be provided with discharge instructions in both verbal and paper form, which informs the subjects that these medications have the potential to impair driving and operation of heavy equipment. Subjects will be given a list of drugs that should be avoided for their interactive potential with MA and will be provided with a phone number to call [name] with questions. A break of at least two days will be required between visits to allow washout. Subjects will be required to take public transit or have a designated driver for each visit. Subjects may be offered a meal from OCTRI nutrition services, snacks or gift card to the VA canteen during each of these visits. Subjects may be asked to be a backup subject for Visits 3 or 4. Double-booking will help ensure the best use of time and resources. If both participants show up for the visit and we do not complete your visit, they will be paid \$50 in prepaid debit cards for your time.

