MA Metabolites: Blood/oral fluid drawn will be stored in a VAPORHCS freezer and then sent to the Center for Human Toxicology at the University of Utah to quantify the level of meth and meth metabolites present in the sample using Gas Chromatography/Mass Spectroscopy. Samples will be shipped via courier on dry ice (NIDA contract N01DA-19-8951). Samples will be recoded with a number (consecutive numbers, 1,2,3,etc) and will be labeled with this number prior to being shipped. No other information will be on the label or be provided to the University of Utah. These samples will be acquired once during V1 and twice each during V3 and V4 for individuals in the MUD group. Samples will be acquired only once during V3 and once during V4 for control subjects, after study drug is administered.

Biorepository Data/Specimen Use: A separate cohort of data/specimens will be pulled from the MARC biorepository and included in the analysis for this project. Data/specimens pulled will be nearly identical to the data used in this project and will include demographics (no identifiers), questionnaire data, information on drug/alcohol abuse, mental health diagnoses, computer task data, imaging data (MRI), coded lab results and saliva samples. Saliva samples will be sent out with the other saliva samples collected for this project and analyzed for methamphetamine metabolites at the University of Utah.

Data Acquisition and Processing

Rating scales: Subjective endpoints (MA-elicited craving, subjective high and intoxication), positive affect, will be measured using self-report surveys administered prior to scanning and again after the scan (Table 1). **MRI Acquisition:** We will use a 3T Siemens Magnetom Prisma scanner and a 32-channel phased array head coil. RSFC (T_2^* -weighted): One T_2^* - weighted echo-planar imaging (EPI) functional run will be acquired. Each run will utilize real-time motion tracking, Framewise Integrated Real-time MRI Monitoring (FIRMM), to ensure at

Instrument	Measures		
Visual Analog Scale for	Methamphetamine		
mood (VAS-today)	effects		
Visual Analog Scale for craving (VAS-crave)	Drug liking		
Addiction Research Center Inventory (ARCI)	Drug effects		
Global Rating of Stimulation (GRS)	Stimulation		
Profile of Mood States (POMS)	Active mood states		
Profile of Mood States-Bi Elevation (POMS-E)	Active mood states		
Rapid Visual Information Processing Task (RVIPT)	Sustained attention		

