Digit Symbol Substitution Task (DSST)	Psychomotor speed; sustained attention		
Controlled Oral Word Association Test (COWAT)	Verbal fluency		
Table 1: Rating scales and instruments.			

least 40 min of motion-free data per run is collected for analysis (Dosenbach et al., 2017). High-resolution anatomical (T_1 -weighted [T_{1w}]): One magnetically prepared rapid acquisition gradient echo (MPRAGE) will be acquired for coregistration with functional images and statistical overlay. The collection of 40 min of high quality fcMRI data will ensure substantial increase in SNR of the connectivity signal and allow for the evaluation single subject changes (Laumann et al., 2015;Gordon et al., 2017).

fMRI Standard Preprocessing: RSFC data will be corrected for B₀ inhomogeneity distortion, gradient nonlinearity distortion, head motion, and registration to pre-processed structural volumes. Gradient nonlinearity distortions will be corrected using scanner-specific field maps. Images will be preprocessed using FSL and software developed in-house by the [name] Laboratory. The motion censoring technique described recently by Power and colleagues, and used by Co-I [name] and colleagues, will greatly reduce the residual effect of head motion on observed time courses. fMRI time courses will be

sampled to the cortical surface mesh, using the extent of overlap with the cortical ribbon as a weighting factor to account for partial volume effects to enable cortical surface-based analyses.

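### At its minimum, the two-day crossover break puts the study methamphetamine dose inside the protocol's own 72 h pre-scan abstention window, and the abstention figures conflict

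*Combined protocol and SAP*

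**What the plan says.** All references are to the combined protocol and SAP.

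- **Break between visits** (Part 2: Visits 3 and 4: Scan Days): "A break of at least two days will be required between visits to allow washout". No half-life or other basis is given.
- **Abstention before scans.** The same section states: "Subjects are asked to abstain from MA for 72 h before the scan". The inclusion criteria for the MUD groups read: "Abstinent from methamphetamine for 48 hours on days of scans". Abstention from Methamphetamine says that MUD subjects will be asked to "abstain from using methamphetamine for 24 hours prior to Visits 3 and 4".
- **Timeline of a scan visit.** The baseline scan comes about 1 h into the visit, dosing follows it, and there is "a second scan 1.5 hours after that". Visits last about 8 h. Under MRI Acquisition, each run is to ensure that at "least 40 min of motion-free data per run is collected for analysis".
- **Order.** Under MA Administration and Randomization, three of every six subjects receive MA at the first dosing visit. That text numbers the dosing visits 2 and 3, while the visit schedule doses at Visits 3 and 4. I use the schedule's numbering.
- **Model.** For Hypotheses 2 and 3, Specific Outcome Measures and Hypotheses names a linear mixed model with scan day and drug as within-subject factors, plus genotype and its interaction. It names no sequence or carry-over term.
- **MA levels.** Under MA Metabolites, MUD subjects are sampled twice at each scan visit, which the Scan Days section places before dosing and after the second scan. For controls: "Samples will be acquired only once during V3 and once during V4 for control subjects, after study drug is administered".

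**The concern.** In a two-period crossover the washout protects the second period from the first. Here the minimum washout can be shorter than the MA-free interval that the same section asks for before a scan. A subject could keep to the abstention request outside the study and still be scanned at Visit 4 inside the 72 h window, because the trial gave the dose.

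Only subjects who receive MA first can be affected this way. Any residual effect would reach their Visit 4 pre-dose scan and their placebo condition, and nobody else's. Scan-day and drug terms describe average period and treatment differences. They do not isolate an effect present in one order only. If residual drug made placebo look partly like MA, the MA-placebo contrast would shrink. If the same fraction remained in both genotypes, the genotype-by-drug contrast behind Hypothesis 2 would shrink in the same proportion.

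**Working it through.** The plan gives no derivation of the two-day figure, so there is nothing to reproduce. The check is clock arithmetic.

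**Inputs.** Hour 0 is the start of Visit 3. The baseline scan starts at 1 h on both days. Scan length *s* is at least 40 min (0.67 h) from the protocol. Total scan time is not stated, so I assume up to 1.5 h. The dose is taken to follow the scan at once; a later dose would shorten the gap to the Visit 4 baseline scan. *S* is the time from the start of Visit 3 to the start of Visit 4 at the minimum break:

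- (a) 48 h start to start: *S* = 48
- (b) 48 h from the end of an 8 h visit: *S* = 48 + 8 = 56
- (c) two clear calendar days, same start hour: *S* = 72

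**Formulas.**

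- Dose time = 1 + *s*
- Dose to Visit 4 baseline scan = (*S* + 1) − (1 + *s*) = *S* − *s*
- Dose to post-placebo scan = (*S* + 1 + *s* + 1.5) − (1 + *s*) = *S* + 1.5

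**Results.**

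| Reading | Dose to Visit 4 baseline scan | Against 72 h | Against 48 h | Against 24 h | Dose to post-placebo scan |
|---|---|---|---|---|---|
| (a) | 46.5–47.3 h | short by 24.7–25.5 h | short by 0.7–1.5 h | met | 49.5 h |
| (b) | 54.5–55.3 h | short by 16.7–17.5 h | met | met | 57.5 h |
| (c) | 70.5–71.3 h | short by 0.7–1.5 h | met | met | 73.5 h |

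The baseline scan is inside 72 h on every reading. The post-placebo scan is inside 72 h on (a) and (b) but not on (c).

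**Who can be affected.** 72 × 3/6 = 36 MA-first completers. The 48 h and 24 h figures are written for MUD subjects, of whom 36 × 3/6 = 18 are MA-first. Whether the 72 h request is meant for controls is not stated.

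**Possible size.** Let *d* be the true MA-placebo difference at the post-dose scan and *c* the fraction of the effect still present on the placebo day. MA-first subjects show *d*(1 − *c*) and placebo-first subjects show *d*. With half in each order the average is *d*(1 − *c*/2), an attenuation of *c*/2. The documents give no half-life, so I assume a range, first-order elimination, effect proportional to residual drug, and every MA-first subject seen at the minimum on reading (a). Residual = 2^(−47/half-life):

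| Assumed half-life | Residual at 47 h | Attenuation *c*/2 |
|---|---|---|
| 8 h | 2% | 0.9% |
| 10 h | 4% | 1.9% |
| 12 h | 7% | 3.3% |
| 15 h | 11% | 5.7% |
| 20 h | 20% | 9.8% |

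At 49.5 h, the time of the post-placebo scan itself, the two ends become 2^(−49.5/8)/2 = 0.7% and 2^(−49.5/20)/2 = 9.0%. The order of magnitude does not change.

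**The case against.** The strongest reply is that there is no single required interval to breach. The protocol gives three, and the 24 h figure is met on every reading. The 72 h statement is a request, while the eligibility criterion is 48 h, and 48 h is missed only on reading (a), by 0.7–1.5 h. The break is a floor, so nobody need be scheduled at it. On clear days the 72 h shortfall is also only 0.7–1.5 h, which a slightly later start would remove. All of this stands. It limits the firm conflict to the 72 h figure at minimum spacing, and it shows that the abstention figures themselves disagree.

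The reply can also say that a different window for study drug may be deliberate. The study maximum is 30 mg, against the 100 to over 500 mg per day that the protocol attributes to active users (30/500 = 6%; 30/100 = 30%). That could justify the difference, but the protocol does not offer it.

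Each visit has its own pre-dose scan. If change from that scan is analysed, stable carry-over would largely cancel. The plan does not say whether the contrast is raw post-dose or change from same-day baseline. Randomization is stratified by genotype, so order should be roughly balanced between genotypes. That guards against a spurious genotype difference but does not remove attenuation.

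A reader might infer that residual drug cannot be checked in controls because they have no pre-dose sample. The documents do not support this. An MA-first control receives placebo at Visit 4, so the planned Visit 4 sample measures residual study MA. A reader might also take the Visit 4 pre-dose scan to be part of the SA 1 baseline. The protocol says only baseline, without naming a visit.

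**Conclusion.** The point holds in limited form. At the minimum break, an MA-first subject's Visit 4 baseline scan falls inside the 72 h window because of the study dose, however the break is counted, assuming both visits start at the same hour under the clear-days reading. About 36 of 72 completers could be affected, or 18 of 36 if the 72 h request applies to MUD subjects only. The stated model does not address an effect confined to one order. The protocol refers to a section on statistical design and power that is not in the document provided, so a sequence term there cannot be ruled out.

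Direct attenuation is probably small: about 1 to 10% of a raw post-dose contrast under the half-lives and worst-case scheduling assumed above, and less if same-day change is analysed or spacing is usually wider. The calculation excludes after-effects of MA that do not track drug level, whose direction is unknown.

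Two stronger readings should be resisted. One is that MA-first MUD subjects necessarily fail the 48 h inclusion criterion: this happens on one of three counts, marginally, and only at the minimum. The other is that the documents show carry-over to be present: they do not. What they show is unreconciled intervals and an analysis that would not reveal carry-over as stated.

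**What to change.** 1. Reconcile the 24 h, 48 h and 72 h abstention figures with each other and with the two-day break, or state why study drug is treated differently. Say whether the 72 h request covers controls. Which interval is right is for the sponsor; this review does not choose one.
2. State how the break is counted: hours from dose to next scan, or clear days.
3. Define the SA 1 baseline as the Visit 3 pre-dose scan and craving score, which precede any study drug.
4. Record hours from the Visit 3 dose to each Visit 4 scan. Use the MA levels already planned at Visit 4 (pre-dose in MUD, post-placebo in MA-first controls) to look for residual drug. No extra sample is needed.
5. State whether the Hypothesis 2 contrast is raw post-dose or change from same-day baseline, and report it by treatment order. With about nine MA-first subjects per group of 18, this is a descriptive check, not a powered test of carry-over.

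The cost is protocol wording, one derived variable and one extra table. Depending on how the intervals are reconciled, scheduling may be slightly less flexible. SA 1 may rest on one baseline scan instead of two, with some loss of precision if both would otherwise have been used.

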MA Administration and Randomization: For Part 2, subjects will randomly receive oral MA (0.25 -0.3 mg/kg; Desoxyn®, Lundbeck) on one visit and placebo on the other. Subjects with weight between 50-60 kg, will receive 15 mg oral dose; 60-80 kg, 20 mg; 80-100 kg, 25 mg; 100+ kg to max weight, 30 mg dose. The VA Portland Research pharmacy will provide MA and identical PBO in tablet form. The pharmacy will maintain a randomization schedule such that for each group of 6 subjects, three will receive MA on visit 2 and three will receive MA on visit 3. Study staff will be blinded to treatment.

Weight (kg)	MA Dose (mg)
50 - 60	15
60 - 80	20
80 – 100	25
100 +	30

Appointment Confirmation: Once subjects are consented, appointment confirmation with occur via phone or email. Appointment confirmation emails may be sent via Azure to subjects. Brief scheduling correspondence may also happen through Azure if the study team is not able to connect with the subject via phone. Subjects will be screened for COVID-19 symptoms during confirmation calls prior to study visits and again at the beginning of each in-person visit along with a temperature check. If any symptoms are revealed, the visit will be rescheduled for at least two weeks or until symptoms are resolved.

Subject Reimbursement: Participants will be paid in the form of Clincards for completing all or partial study procedures and will be paid at the end of the visit. For Clincard payments, subjects will be registered by name in the Clincard online system and issued a loaded debit card. Participants will be reimbursed \$40 for the first and second visits, \$100 for the third visit and \$125 for the fourth visit (total = \$305) in the form of prepaid debit cards. Participants who need to combine visits or break visits into multiple sessions will be prorated based on completion of tasks during the session. Subjects will also be offered Trimet day use tickets if they are using public transportation. If both subjects show-up to a double-booked appointment, the subject not undergoing imaging will receive a \$50 prepaid gift card for the inconvenience and be rescheduled. Subjects may be asked to repeat procedures if data isn't usable. If an entire visit is repeated, then they'll be paid for the whole visit at the regular amount again. They will be paid at a pro-rate of \$20/hr for any other repeated procedures or partial visits.

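### At some body weights the fixed methamphetamine doses fall outside the stated 0.25–0.3 mg/kg, and the allocation sentence numbers the dosing visits differently from the visit schedule

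*Combined protocol and SAP*

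**What the plan says.** The dose text is in the combined protocol and SAP, section MA Administration and Randomization. It states that "subjects will randomly receive oral MA (0.25 -0.3 mg/kg", with MA on one visit and placebo on the other. It then sets fixed doses: "Subjects with weight between 50-60 kg, will receive 15 mg oral dose; 60-80 kg, 20 mg; 80-100 kg, 25 mg", and for the heaviest participants "100+ kg to max weight, 30 mg dose". The table below it repeats the same four doses, and its last row is open-ended from 100 kg. On supply it says "The VA Portland Research pharmacy will provide MA and identical PBO in tablet form". The paragraph on decisionally impaired participants also gives 30 mg as the maximum dose.

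The eligibility criteria set no weight limit. Entry to Part 2 is described under Enrollment: "Individuals will then be screened into Part 2 based on their genotype and if they have no contraindications for methamphetamine administration or MRI".

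On allocation, the same dosing section says that in each group of six "three will receive MA on visit 2 and three will receive MA on visit 3". In the visit table, the row that begins "Study Drug or Placebo" is ticked at visits 3 and 4 only. The dosing days are described under "Part 2: Visits 3 and 4: Scan Days". The section MA Metabolites places the controls' post-drug samples at V3 and V4. Visits 1 and 2 form Part 1, consent and screening.

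**The concern.** The MA dose is the study intervention. The mg/kg range and the band list describe the same dose, so they should agree at every weight that can be enrolled. Where they do not, a reader of the protocol, or of a report that quotes the mg/kg range, is told something other than what the participant received. At a shared band edge the text lists two doses for one participant.

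The visit labels raise a similar question. The allocation sentence names a screening visit at which no drug is given and omits visit 4, at which it is. Visit 3 is the later dosing day in that sentence but the earlier one in the schedule. Scan day and drug are the two within-subject factors in the planned mixed model, so the label that links the pharmacy list to the dosing day should be unambiguous.

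**Working it through.** **Inputs.** Stated range 0.25–0.3 mg/kg; bands 50–60, 60–80, 80–100 and 100+ kg; doses 15, 20, 25 and 30 mg. All are from MA Administration and Randomization.

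**Formulas.** Dose per kg = D / weight. Reading the upper limit strictly as 0.30, dose D is in range for weights from D/0.30 to D/0.25.

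| Band (kg) | Dose (mg) | mg/kg at lower edge | mg/kg at upper edge | Weights in range (kg) |
|---|---|---|---|---|
| 50–60 | 15 | 15/50 = 0.300 | 15/60 = 0.250 | 50.0–60.0 |
| 60–80 | 20 | 20/60 = 0.333 | 20/80 = 0.250 | 66.7–80.0 |
| 80–100 | 25 | 25/80 = 0.3125 | 25/100 = 0.250 | 83.3–100.0 |
| 100+ | 30 | 30/100 = 0.300 | no edge given | 100.0–120.0 |

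The stated range is reproduced exactly in the first band, and in the last band up to 120 kg. It is not reproduced in the lower part of the two middle bands or above 120 kg.

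**Size above the range (strict reading).**
- 20 mg at 60 kg: 20 − 0.30 × 60 = 2.0 mg over; 0.3333/0.30 − 1 = 11.1%.
- 25 mg at 80 kg: 25 − 0.30 × 80 = 1.0 mg over; 0.3125/0.30 − 1 = 4.2%.
- Both excesses shrink to zero, at 66.7 and 83.3 kg.
- Width affected: (66.67 − 60)/20 = one third of the 60–80 kg band and (83.33 − 80)/20 = one sixth of the 80–100 kg band. Together that is 6.67 + 3.33 = 10 kg of the 70 kg between 50 and 120 kg. This is a share of the scale, not of participants.

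**Could another listed dose fit?** Not strictly inside those zones. At 62 kg the range is 0.25 × 62 = 15.5 to 0.30 × 62 = 18.6 mg, between the 15 and 20 mg doses. At 82 kg it is 20.5 to 24.6 mg, between 20 and 25 mg.

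**Size below the range.** The documents give no maximum weight, so these two weights are assumed for illustration.
- 125 kg: 30/125 = 0.240 mg/kg; 0.25 × 125 − 30 = 1.25 mg under.
- 130 kg: 30/130 = 0.231 mg/kg; 0.25 × 130 − 30 = 2.5 mg under.

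**Rounding variant.** If the upper limit is read to one decimal, as it is printed, 0.333 and 0.3125 both round to 0.3 and the upper departures vanish. The departure above 120 kg remains. Rounding the lower limit to its two printed decimals only moves its start to 30/0.245 = 122.4 kg.

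**Shared edges.**
- 60 kg: 15 or 20 mg (0.250 or 0.333 mg/kg).
- 80 kg: 20 or 25 mg (0.250 or 0.3125 mg/kg).
- 100 kg: 25 or 30 mg (0.250 or 0.300 mg/kg). Both lie in range, so the range cannot settle this edge.

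**Visit labels side by side.**

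| Place | Visits with study drug |
|---|---|
| Allocation sentence | 2 and 3 |
| Visit table | 3 and 4 |
| Part 2 visit description | 3 and 4 |
| MA Metabolites | V3 and V4 |

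Three places agree against one. Renumbering the sentence leaves three participants with MA on the first dosing day and three with MA on the second.

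**The case against.** The best defence on dose is that the band list is the working rule and the mg/kg figure is a short description of it. The list is the same in text and table, its ceiling is repeated elsewhere, and apart from the exact edges every weight from 50 kg up maps to one dose. Fixed tablet doses can only approximate a mg/kg range. With 0.3 read as rounded, nothing exceeds the range at all. That reading is possible and has to be stated. It is not certain, because the lower limit of the same expression has two decimals, and it leaves the weights above 120 kg and the shared edges unresolved.

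The low side can also be contested. The text refers to some maximum weight, and 30 mg stays in range to 120 kg, so a maximum at or below 120 kg would remove the departure. The table row is open-ended, however, and no such maximum is written. The unstated maximum and the lack of a band below 50 kg are missing detail, not contradictions.

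On visits, the paragraph opens by limiting itself to Part 2, and visits 1 and 2 may be combined, which would make the dosing days the second and third attendances. That may explain the numbering. The schedule still calls the dosing days 3 and 4, and payment is set separately for a third and a fourth visit.

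A reader might infer that the bands fail in general, that the genotype comparison is biased, or that someone would be dosed at screening. The documents support none of these. Most weights are in range, no weight distribution by genotype is given, and every description of the dosing days puts them in Part 2.

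**Conclusion.** The point holds in a limited form. At some weights the bands and the stated range disagree:

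- Up to 11.1% (2 mg) over at 60 kg and 4.2% (1 mg) over at 80 kg, if 0.3 is read strictly; nothing over if it is rounded to one decimal.
- Under 0.25 mg/kg above 120 kg, if anyone that heavy is enrolled.
- Two listed doses at exactly 60, 80 and 100 kg, on either reading.

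The share of participants affected cannot be worked out, because the documents give no weight distribution. The visit numbers in the allocation sentence conflict with the schedule. This is probably leftover numbering, and the 3:3 allocation stands. No hypothesis test, sample size or genotype contrast is shown to change. These are small errors in the description of the intervention and of its allocation, worth correcting because they are in the operative text.

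**What to change.** The sponsor should reconcile the stated mg/kg range with the weight bands and their shared edges, and say whether 0.3 is a rounded figure and what the maximum weight is. Which statement is right is for the sponsor to decide. The visit numbers in the allocation sentence should be reconciled with the visit table, the Part 2 visit description and MA Metabolites, and the pharmacy randomization list checked for the same visit labels. The cost is amendment text and one check of the list. No extra participants or procedures are needed.
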